4. SRA+HC+GRC

Random assignments will be generated using a standard random number generator with uniform distribution to the four groups by the Clinical Genomics Study Unit (CGSU) data manager. The research staff (CRC at site) will use this randomization schema to inform participants of their group assignment.

Follow up visits:

6-week and 3-month – At 6 weeks and 3 months after the baseline visit, participants will be asked to complete selected surveys online (Table 1). The 6 week survey must be completed after the counseling visit and before Health Coaching begins.

6-month – Six months from the baseline visit, participants will return to the clinic to have weight, BP and waist circumference measured (same procedures as baseline visit). Medications will be reviewed and AE's assessed.

Female subjects will be asked if they are currently pregnant and this will be documented.

They will also complete the required surveys as listed, either before their scheduled visit or during their visit at the clinic.

12-month- Twelve months from the baseline visit, participants will return to the clinic for a final visit to have weight, BP and waist circumference measured (same procedures as baseline visit). Medications will be reviewed and AE's assessed.

Lab values from the EMR will be documented for fasting glucose, TC, HDL, LDL, TRIG CRC will check in EMR prior to each subject's 12-month visit. If lab values as stated above are not available from the last 6 months of study participation , then a lipid panel (TC, HDL, LDL, TRIG) and either a FBG or HbA1c will be ordered. Female subjects will be asked if they are currently pregnant and this will be documented.

They will also complete the required surveys as listed, either before their scheduled visit or during their visit at the clinic.

Window of ±one week were allowed for all follow up visits. In order to maximize power and considering

Genetic Risk Testing and Health Coaching for CHD and T2D

Duke IRB# Pro00039569 NCT01884545

recent findings on the stability of metabolic clinical markers absent behavior change, statistical analyses will employ extended inclusion windows for study time-points. Statistical analyses will include: +/-3 weeks for the 6 week survey, +/-7 weeks for the 3 month survey, and +/-11 weeks for the 12 month survey.

Table 1.

STUDY VISITS	GROUP 1	GROUP 2	GROUP 3	GROUP 4

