8.1. Sample Size/Power Calculation

The objective of the power analysis was to determine the minimum sample size needed to reject the null hypothesis that the three-way genetic information by health coaching by time interaction was equal to zero in the context of a longitudinal general linear mixed model. The model was assumed to have two levels of genetic information (present or absent), two levels of health coaching (present or absent), and five levels of time (0, 1.5, 3, 6 and 12 months after randomization). In producing the required sample-size estimates, we further assumed that each of the four group means over time would take on standardized mean values. The type I error rate was set to be no greater than .025 as there will be two primary analyses. Controlling each one at no greater than .025 controls the overall experiment type I error rate to be no greater than .05. Calculations indicated that with a sample size of 99 subjects per group, or 396 total, the power to reject the null hypothesis concerning the three-way interaction was .80. Assuming an attrition rate of at most 15% and the current pilot diabetes study attrition of 11%, over the 12 month time period we calculated a possible required sample size of $(396/.86)=460$ to attain the target sample of 400. Sample size calculations are not provided for detecting the direct effects or interactive effects of the two interventions pooled over time, primarily because we expect the genetic information by health coaching interaction to change over time, as reflected in the three-way interaction.

Due to delayed/slow recruitment the sample size is revised as following (modification approved in contract amendment):

A reduced sample size, but collecting data out to 12 months as planned:

- a. Coming from the stance that we want to preserve as much of the original thinking behind the power analysis as possible, we eliminated the calculation and testing of the three way

interaction which was originally planned. This three way interaction said that the interaction of Health Coaching and genetic testing peaks at 6 months. The idea was that there was a synergy between genetic testing and health coaching which would push health behavior means for the subjects receiving both components to far greater than the individual effects of either one. Elimination of the three way interaction takes away our ability to say when this occurs (time).

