Pattern	Type I error rate	Power	Within Person Correlation	Sample Size per Group	Total Sample Size
1	.025	.80	.350	25	100
1	.025	.85	.350	27	108
2	.025	.80	.350	44	176
2	.025	.85	.350	49	196
3	.025	.80	.350	56	224
3	.025	.85	.350	63	252

- b. Means for the four groups pooled across time showing JUST the coaching by genetics testing interaction for each pattern.
- c. Examining the health coaching by time and the genetic testing by time interactions. Assuming the same means over time for pattern 2, the means for the two interactions would be as shown in the two tables immediately below.

Health coaching by time interaction for pattern 2

	NO HC	HC
0	0.05	0.05
1.2	0.15	0.5
3	0.275	0.95
6	0.125	1.5
12	0.05	0.85

Genetic testing by time interaction for pattern 2

	No Genetics	Genetics
0	0.05	0.05
1.2	0.225	0.425
3	0.425	0.8

6	0.525	1.1
12	0.225	0.675

d. Results of power calculations when the three way interaction for the groups, as well as the three way interaction for time by health coaching by genetic testing are eliminated. These are the power for detecting the interaction which is the smallest (the genetic testing one).

Pattern	Type I error rate	Power	Within Person Correlation	Sample Size per Group	Total Sample Size
2	.025	.80	.350	43	172
2	.025	.85	.350	49	196

While we will have lost the power to examine a 3-way interaction (health coaching by genetic risk testing by time), with the participants, we will still be able to:

- 1) Examine 2 way interaction effects of health coaching by time and genetic risk testing by time (estimated minimum sample needed 172-196);
AND/OR
- 2) Examine the 2 way interaction of health coaching and genetic risk testing (comparative effectiveness without time point considered in interaction; estimated sample needed 176-196).

Assuming an attrition rate of at most 15% the required minimum sample size is 212.

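### The revised sample sizes in 8.1 come from a five-visit model with a coaching effect at 6 weeks, but coaching has not begun by then and diet and activity are not collected at that visit

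*Combined protocol and SAP*

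**What the plan says.** Section 8.1 describes a longitudinal mixed model with "five levels of time (0, 1.5, 3, 6 and 12 months after randomization") and assumes that "each of the four group means over time would take on standardized mean values". Alpha is .025 per analysis: "The type I error rate was set to be no greater than .025 as there will be two primary analyses". The column headed "Within Person Correlation" gives .350 throughout.

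After the three-way test was dropped, 8.1 gives two sizes for pattern 2:

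- 172-196 (43-49 per group) for the two interactions with time, at power .80-.85. Item d says this is set by the smaller of the two, genetics by time.
- 176-196 (44-49 per group) for coaching by genetics pooled over time: "comparative effectiveness without time point considered in interaction; estimated sample needed 176-196".

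Allowing for 15% attrition, 8.1 gives a minimum of 212. Section 5.1 plans to enrol 250.

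The pattern 2 means are printed as two margins, "Health coaching by time interaction for pattern 2" and "Genetic testing by time interaction for pattern 2". Item b announces the four-group means, but no values appear in the available text, possibly because of PDF conversion.

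On timing, 5.3.1 (Follow up visits) says: "The 6 week survey must be completed after the counseling visit and before Health Coaching begins". Table 2 marks diet and physical activity at baseline, 3, 6 and 12 months only. Section 8.2 refers to measures at five time points but gives the time variable four values: 0, 3, 6 and 12 months.

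**The concern.** The planning means credit coaching with a benefit at a survey that the schedule places before the first coaching call. The main behavioural outcomes are not collected at that survey in any case. A sample size is meaningful only for the visits and contrasts that will enter the model. If the second row drops out, or carries no coaching effect, the stated 0.80-0.85 power is not the power of the planned analysis. This affects both two-way questions that the revised design says it can still answer.

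**Working it through.** **Inputs.** From 8.1: SD 1 (standardised means), correlation 0.35, alpha 0.025 and the two printed margins. Sidedness is not stated, so F tests and two-sided z are used. Compound symmetry is assumed. The row labelled 1.2 is taken as the 6-week visit (1.5 months in the model description).

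**1. Differences in the printed margins (0, 6 weeks, 3, 6, 12 months)**

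- Coaching minus none: 0, 0.35, 0.675, 1.375, 0.80. The 6-week value is 0.50 - 0.15 = 0.35.
- Genetics minus none: 0, 0.20, 0.375, 0.575, 0.45.

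The schedule contradicts only the coaching value at 6 weeks. Genetic results are given at the risk assessment visit, which precedes the 6-week survey.

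**2. Genetics by time (stated: 43 and 49 per group)**

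With n per group, noncentrality = n × SS / (1 - 0.35). SS is the sum of squared deviations of the visit differences from their mean. The F test has T - 1 and (4n - 4)(T - 1) df.

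- Five visits: mean 0.32, SS = 0.20175, noncentrality 0.3104n. Power at 43 is 0.77, and 46 and 51 per group are needed for 0.80 and 0.85 (184 and 204 in total). The plan's 43 and 49 are approached but not reproduced.
- Four visits: mean 0.35, SS = 0.18375, noncentrality 0.2827n. Power at 43 is 0.77, and 47 and 52 per group are needed (188 and 208).

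Dropping the visit costs about one participant per group. The rest of the gap is already present on five visits.

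Coaching by time is not limiting. It needs about 10 per group as printed and 8 with the 6-week coaching difference set to zero.

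**3. Coaching by genetics pooled over visits (stated: 44 and 49 per group)**

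Let I be the difference of differences averaged over T visits. Then s² = (1 + (T - 1) × 0.35)/T, and n = (z + z)² × 4s²/I², where (z + z)² is 9.505 for power 0.80 and 10.744 for 0.85. Five visits give s² = 0.48.

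Back-solving: I = √(9.505 × 1.92/44) = 0.644 and √(10.744 × 1.92/49) = 0.649. The margins do not fix I, so a direct reproduction is not possible. Two sets of cell means, both agreeing with both printed tables, show the spread.

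*Set A (assumption: genetics acts only with coaching).* By visit, I is twice the genetics margin: 0, 0.40, 0.75, 1.15, 0.90, with mean 0.64.

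| Handling of 6 weeks | mean I | s² | n per group (0.80 / 0.85) | power at 44 |
|---|---|---|---|---|
| As planned | 0.64 | 0.48 | 44.6 / 50.4 | 0.79 |
| Interaction set to 0 | 0.56 | 0.48 | 58.2 / 65.8 | 0.66-0.67 |
| Visit dropped | 0.70 | 0.5125 | 39.8 / 45.0 | 0.84 |

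*Set B.* The 6-week cells are 0.05 (neither), 0.25 (genetics only), 0.40 (coaching only) and 0.60 (both). They return the printed margins 0.15, 0.5, 0.225 and 0.425, and the interaction is 0.60 - 0.40 - 0.25 + 0.05 = 0. With by-visit contrasts 0, 0, 0.85, 1.45 and 0.90, the mean is again 0.64. Setting the 6-week interaction to zero changes nothing (44.6). Dropping the visit gives mean 0.80 and 30.4 per group at 0.80.

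More generally, hold pooled I at 0.644 and keep the 6-week cell means non-negative. The 6-week contrast can then lie anywhere from -0.2 to 1.0. Setting it to zero gives about 39 to 93 per group at 0.80.

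**4. Against enrolment**

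250 × 0.85 = 212.5, about 53 per group. At 53, genetics by time on four visits has noncentrality 0.2827 × 53 = 14.98 and power 0.86. Inflating 188 and 208 for 15% attrition gives 188/0.85 = 221.2 (222) and 208/0.85 = 244.7 (245). Both exceed 212 and both are below 250.

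**The case against.** The best defence is that the flawed row does little damage. The coaching-by-time table does not set any stated size: 172-196 is driven by genetics by time, and coaching by time has power near 1 either way. The 0.35 is a coaching difference averaged over genetics, so it cancels from the coaching-by-genetics contrast and is not itself an input to 176-196. If the 6-week visit is simply left out, as Table 2 implies, Set A gives higher power than planned. Enrolment of 250 leaves room for the genetics-by-time figures.

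All of this stands, and it keeps the point small. It does not remove the mismatch: the sizes are stated for a five-visit model that cannot be fitted to diet and activity, and 8.2 gives two different visit counts.

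A second defence is that some coaching effect at 6 weeks is conceivable. Coached participants complete a goals form and receive the coaching folder at the risk assessment visit, and the analysis window of ±3 weeks admits surveys up to week 9. Neither is offered in 8.1 as a basis for 0.35 SD.

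**Conclusion.** The inconsistency is established. The sizes 172-196 and 176-196 come from five visits with a 0.35 SD coaching difference before coaching begins, and they do not correspond to the visits at which diet and activity are collected.

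For genetics by time the correction is about 188-208 against 172-196, given the printed means, compound symmetry, correlation 0.35 and alpha 0.025. Only about one participant per group of that is due to the missing visit.

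For coaching by genetics, a reader might infer that 176-196 depends on an impossible effect and is too small. There is an argument for this. If genetics alone is never harmful, the margins cap pooled I at 0.64, close to the 0.644 that 44 per group requires, and that cap includes 0.40 at 6 weeks. But 8.1 does not state that condition, and its synergy rationale allows each component an effect of its own. Even under Set A, 6 weeks supplies 0.40 of a summed 3.20, or 12.5%, and dropping the visit raises power to 0.84. No shortfall is shown, and the direction stays open until the four-group means by visit are available. This is a minor but specific correction.

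**What to change.** Reconcile 5.3.1 (order of the 6-week survey and coaching), Table 2, the planning means in 8.1 and the visit list in 8.2, so that one set of time points is used throughout. Print the pattern 2 means for all four groups at each visit and correct the 1.2/1.5 label. From those means, recompute both two-way tests on the visits actually analysed (0, 3, 6 and 12 months for diet and physical activity). Any model that keeps the 6-week visit should justify its coaching effect there or set it to zero. Then restate 172-196, 176-196 and the minimum of 212, or keep those sizes and restate their power.

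The cost is one recalculation and a revised table in 8.1, with a matching edit to 8.2. Enrolment and data collection do not change.

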8.2. Analysis Plan

Demographic characteristics of the sample (income level, age, gender, race/ethnicity, educational level) will be provided using descriptive statistics to describe the overall sample and by group to ensure that randomization was effective. Distribution of variables will be determined prior to further statistical analysis. SAS software (80) will be used for all analyses.

To address the primary aims, mixed models will be used. The first aim is to determine the direct and interactive effects of genetic risk information incorporated with standard CHD/T2D risk counseling and a health coaching intervention for CHD/T2D on behavior change (diet, physical activity) in AF primary care patients over 12 months. The goals of the statistical analysis will be to quantify: (1) the extent to which genetic risk counseling influences the trajectory of change in physical activity and diet measures from baseline to 3, 6, and 12 months; and (2) the extent to which the genetic risk information augments the trajectory of the effects of health coaching on diet and physical activity measures over the same time period. We will fit two general linear mixed models to these data (81), with

physical activity and diet measures at each of the five points in time. For either model, there will be three independent variables: genetic risk information (G) with values of 1 or 0, health coaching (HC), also with values of 1 or 0, and time since randomization, with values of 0, 3, 6, and 12 months. Within the context of the linear mixed model, we should observe a statistically significant three way interaction of time by genetic information by health coaching. The particular type of longitudinal model selected for analysis will depend upon preliminary analyses of the data. For example, a subject specific (also called hierarchical) model with random intercept and slope assumes that within subject variances increase or decrease over time. A model hypothesizing only a random intercept does not assume that within subject variances show this pattern. Another consideration will be the extent of missing data; some longitudinal models are better than others at handling missing data.

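### Labs are scheduled at only two times and 8.2 does not adjust for baseline, so the power in 8.1 does not describe their genetics-by-time test, which is valid but inefficient

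*Combined protocol and SAP*

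**What the plan says.** **Power (8.1).** The design assumed "five levels of time (0, 1.5, 3, 6 and 12 months after randomization". After slow recruitment the sample was reduced and "we eliminated the calculation and testing of the three way" interaction. The revised calculation prints pattern-2 means at five times and gives 43 per group for power .80 and 49 for .85 (alpha .025, within-person correlation .350), with the note "These are the power for detecting the interaction which is the smallest (the genetic testing one". It adds: "Assuming an attrition rate of at most 15% the required minimum sample size is 212". Section 5.1 plans 250.

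**Analysis (8.2).** The primary mixed model has three independent variables: genetic information, health coaching and time, with month 0 as one of the time values. No baseline covariate or constraint is named. The same analysis is then applied to seven metabolic outcomes, four of which are labs: fasting glucose, LDL, triglycerides and total cholesterol. On model choice, 8.2 says: "The particular type of longitudinal model selected for analysis will depend upon preliminary analyses of the data".

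**Schedule.** Table 2 marks labs at baseline and 12 months only; SBP, weight and waist are also measured at 6 months. Section 5.3.1 takes the 12-month labs from the medical record and orders new ones only if none exist from the last six months of participation.

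**Baseline as a covariate.** It appears once, in the 8.2 regression of 6-month diet or activity in the two genetic-testing groups. The reason given there for the simpler model is that only two time points exist.

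**Three-way term.** Despite 8.1, the analysis plan still states that "we should observe a statistically significant three way interaction of time by genetic information by health coaching".

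**The concern.** With two times and baseline means free to differ between arms, the genetics-by-time term is algebraically the between-arm difference in mean change. Subtracting baseline in full adds noise unless the correlation is high. The five-time figures in 8.1 therefore do not apply to four of the seven metabolic outcomes, and no other power is given for them. A null genetics result on labs could partly reflect the form of the analysis, although the plan already uses a more efficient form elsewhere.

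**Working it through.** **Inputs.** From 8.1: pattern-2 difference (genetics minus no genetics) d = 0, 0.2, 0.375, 0.575, 0.45 at the five times; rho = .35; alpha = .025 (taken as two-sided). Assumed: SD 1 (the means are called standardized) and equal correlation between all times. Applying these to labs is also an assumption, since 8.1 framed them as "push health behavior means for the subjects receiving both components" and so on, that is, for behaviour. With n per group, each genetics level has 2n participants, so a contrast with variance v per person has noncentrality n·d²/v.

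Analysed n per group: 250 × 0.85 / 4 = 53; 212 × 0.85 / 4 = 45; 43 is the figure printed in 8.1.

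**Step 1: the plan's own figure.** For five times, noncentrality = n·Σ(d − d̄)²/(1 − rho), on 4 and 4(4n − 4) df. Here d̄ = 0.32 and Σ(d − d̄)² = 0.20175.
- n = 43: 43 × 0.20175 / 0.65 = 13.35, power 0.77 (printed .80)
- n = 49: 15.21, power 0.83 (printed .85)
- n = 53: 16.45, power 0.87

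The printed rows are not exactly reproduced; this formula needs 46 and 51 per group. The comparisons below use one set of assumptions throughout, so their ordering is unaffected.

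**Step 2: labs as planned and with baseline adjustment.**
- Unadjusted change: v = 2(1 − rho) = 1.30
- Baseline-adjusted: v = 1 − rho² = 0.8775

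At n = 53 and d = 0.45, the noncentralities are 53 × 0.2025 / 1.30 = 8.26 and 53 × 0.2025 / 0.8775 = 12.23.

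| n per group, d = 0.45 | Unadjusted | Adjusted |
|---|---|---|
| 43 | 0.63 | 0.81 |
| 45 | 0.65 | 0.83 |
| 53 | 0.73 | 0.89 |

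Power of 0.80 needs 62 per group unadjusted and 42 adjusted.

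**Step 3: lab timing.** A value recorded as the 12-month lab may date from months 6 to 12, where the printed difference runs from 0.575 to 0.45. The midpoint, (0.575 + 0.45) / 2 = 0.5125, is an assumption.

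| d (rho .35) | 43 per group, unadjusted | 53, unadjusted | 53, adjusted |
|---|---|---|---|
| 0.45 | 0.63 | 0.73 | 0.89 |
| 0.5125 | 0.75 | 0.84 | 0.96 |
| 0.575 | 0.85 | 0.92 | 0.99 |

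**Step 4: correlation** (d = 0.45, 53 per group).

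| rho | Unadjusted | Adjusted |
|---|---|---|
| .2 | 0.63 | 0.86 |
| .35 | 0.73 | 0.89 |
| .5 | 0.85 | 0.94 |
| .7 | 0.98 | 0.99 |

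Since 2(1 − rho) − (1 − rho²) = (1 − rho)², the adjusted variance is smaller at every rho below 1. The unadjusted test reaches 0.80 at rho of about .44.

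**Step 5: what is not affected.** Having few visits is not in itself the cause: months 0 and 6 alone would give 0.92 at 53 per group. SBP, BMI and waist, on months 0, 6 and 12, have 0.82 at 43 and 0.90 at 53 per group. Coaching by time on labs (12-month difference 0.85 − 0.05 = 0.80) has 0.99 at 43 per group.

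**The case against.** **No lab power was claimed.** The means were framed for behaviour, section 5 calls the primary outcomes behavioural, and no lab effect, SD or correlation is printed. This stands: the figures above are conditional on carried-over inputs. But Table 2 and 8.2 also place the clinical outcomes in the primary analysis, and 8.1 does not limit its power statement to behaviour.

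**Power of 0.73 is the low end for timing.** This stands. A reader might infer from Table 2 that the labs are underpowered at 0.73. The six-month acceptance rule in 5.3.1 does not support that as a single figure: the range is 0.73 to 0.92 at rho .35 and 53 per group.

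**Labs may be highly correlated over time.** Section 5.3.1 itself appeals to the stability of metabolic markers, which points to a higher rho and a smaller gap. This also stands, and the gain could be slight.

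**The model is left open.** 8.2 defers the choice of longitudinal model, and the documents never use the term change score. That reading is an inference from the listed terms. However, the considerations 8.2 mentions are random intercept versus random slope and the handling of missing data; neither brings in baseline adjustment.

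**The weakness is not specific to labs.** Correct. Under the same assumptions, baseline adjustment would raise the five-time test at 53 per group from 0.87 to 0.99. This argues for one change to all primary models rather than a separate lab model.

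**Conclusion.** The point holds as a matter of efficiency and labelling. For the four lab outcomes, the genetics-by-time test in 8.2 is an unadjusted difference in mean change, given complete data and unconstrained baseline means, and the .80/.85 in 8.1 is not its power. At the printed inputs, carried over by assumption, baseline adjustment raises power at 53 per group from 0.73 to 0.89 (difference 0.45) or from 0.84 to 0.96 (difference 0.5125). The gain is larger at lower correlation and almost nil at .7.

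Two stronger readings should be resisted. The planned analysis is not biased or invalid. Nor do the documents show that the lab comparisons are underpowered, because true lab effects and correlations are not given and, under lab timing or correlation that the plan allows, the unadjusted test exceeds 0.80.

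The conflict over the three-way interaction needs no arithmetic. 8.1 removes the test and 8.2 expects it to be significant. It affects every primary outcome and is a separate matter from lab power.

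**What to change.** 1. In 8.2, fit the primary mixed models with arm means constrained equal at baseline, which randomisation justifies. For complete two-time lab data this is equivalent to adjusting the 12-month value for baseline, as the plan's 6-month regression already does. It also keeps participants with a value at only one visit. That matters for fasting glucose, because 5.3.1 accepts HbA1c in its place.
2. In 8.1, label the stated power as applying to the five-time behavioural assumption. Add lab power on the Table 2 schedule over a range of rho (for example .2 to .7) and of lab timing (months 6 to 12).
3. Reconcile 8.1 and 8.2 on whether the three-way interaction is tested.

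The cost is analysis-plan wording and a re-run of the power table. No visits, samples or participants are added, and one model form still serves all outcomes. The only drawback is that the stated lab power becomes a range, part of which may look less favourable than .80.

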The second part of the primary analysis will determine the direct and interactive effects of genetic risk information incorporated with standard CHD/T2D risk counseling and a health coaching intervention for CHD/T2D on metabolic outcomes (fasting blood glucose, SBP, BMI, waist circumference, LDL, triglycerides, total cholesterol) over 12 months. The statistical analysis will be the same as above except that the dependent variables will be fasting blood glucose, SBP, BMI, waist circumference, LDL, triglycerides, and total cholesterol.

To address Aim 2, we will examine the mediating effects of level of CHD/T2D genetic risk (number of risk alleles) and consequent reclassification of FRS in the case of CHD risk (decreased, neutral, or increased) on behavior change (diet, physical activity) at 6 months. The goal of this analysis is to quantify the extent to which subgroups of patients exhibit different levels of change in diet and physical activity behavior at 6 months post randomization depending on reclassification of FRS and T2D risk level. We also want to know if the differences depend on whether or not the genetic results were delivered in the context of health coaching. For these analyses, we will use results from only the two groups of patients randomized to receive genetic testing (n=200). Because we will have only two points in time, we will use the simpler linear regression model, with the dependent variable being either diet or physical activity collected at 6 months post randomization. There will be six independent variables: the outcome measured at baseline (a covariate), the results of the genetic testing (entered as two dummy coded variables), a dummy coded variable to indicate the presence or absence of health coaching, and two dummy coded variables representing the interaction of health coaching and the results of genetic testing. We are particularly interested in comparing the diet and physical activity changes of patients whose genetic test results move their Framingham risk or T2D levels either up or down (based on number of higher-risk alleles) to those whose genetic

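### Read together, sections 8.1 and 8.2 average the baseline visit into the retained coaching-by-genetics test; this shrinks the estimate and costs efficiency, seriously so for the laboratory outcomes

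*Combined protocol and SAP*

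**What the plan says.** Section 8.1, after the recruitment shortfall, reports that "we eliminated the calculation and testing of the three way" interaction. Two kinds of test remain, joined by and/or: each intervention by time, or the option to "Examine the 2 way interaction of health coaching and genetic risk testing (comparative effectiveness without time point considered in interaction". Item (b) of that section describes what the second option rests on: "Means for the four groups pooled across time showing JUST the coaching by genetics testing interaction for each pattern". The planning model has "five levels of time (0, 1.5, 3, 6 and 12 months after randomization", so baseline is one of the pooled visits. The two pattern 2 tables put every column at 0.05 at time 0, which is a zero effect at baseline. On alpha, "The type I error rate was set to be no greater than .025 as there will be two primary analyses".

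Section 8.2 sets out the mixed models. "For either model, there will be three independent variables: genetic risk information (G) with values of 1 or 0"; the others are health coaching and "time since randomization, with values of 0, 3, 6, and 12 months". No baseline covariate is listed. The section still expects a significant three-way interaction and never writes out the two-way model that 8.1 retains. For the metabolic outcomes, "The statistical analysis will be the same as above except that the dependent variables will be fasting blood glucose" and the other clinic and laboratory measures. Baseline does appear as a covariate later in 8.2, but only in the separate 6-month regression within the genetic-testing arms.

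Table 2 gives the visits: diet and activity at 0, 3, 6 and 12 months; weight, waist and blood pressure at 0, 6 and 12; laboratory tests at 0 and 12.

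**The concern.** A single coaching-by-genetics coefficient fitted across all visits is a weighted average of the interaction at each visit. Before any intervention that interaction has expectation zero by randomisation. Including baseline therefore pulls the estimate towards zero, and chance baseline imbalance enters it with the weight of one visit. The pooled direct effects of genetics and coaching are affected in the same way. The by-time tests are not.

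At stake is the synergy question, which 8.1 describes as the idea behind the design. The shrinkage also depends on how many visits an outcome has, so a constant interaction of one size would be reported at three different sizes. A null result on the laboratory outcomes could not be told apart from dilution and low power.

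**Working it through.** **Inputs from the documents.** Alpha .025 (sidedness not stated; two-sided taken), within-person correlation ρ = .350, and pattern 2 needing 44 per group for power .80 and 49 for .85, all from 8.1. Visits are from Table 2. Power is evaluated at 53 per group, since 212/4 = 53 and 250 × .85/4 = 53.1.

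**Assumptions.** SD 1 (8.1 uses standardized means), compound symmetry, complete data, normal approximation.

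**Formulas.** For k visits including baseline and m = k − 1 after it:
- Pooled over all visits: V = (1 + (k − 1)ρ)/k; a constant interaction is estimated at (k − 1)/k of its size.
- Post-baseline mean with baseline covariate: V = (1 + (m − 1)ρ)/m − ρ².
- n per group = 4V(2.2414 + z)²/D², with z = 0.8416 for power .80. The standard error of the interaction is √(4V/n).

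**Reproducing the plan's 44.** The four pooled cell means are not in the text, so D must be inferred. The pattern 2 genetics table gives differences of 0, 0.20, 0.375, 0.575 and 0.45, mean 0.32. If genetics acts only with coaching, the interaction is twice that, D = 0.64. With V = (1 + 4 × .35)/5 = .48:
- n = 4 × .48 × (3.083)²/0.64² = 44.6, and 50.4 for power .85, against the stated 44 and 49.
- Averaging only the four post-baseline visits (D = 0.80) gives 30.4, or 23.2 with baseline adjustment.

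The stated 44 thus appears to include the baseline zero. Solving back from 44 gives a pooled D of 0.644, or a constant post-baseline interaction of 0.644 × 5/4 = 0.805.

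**Dilution and relative sample size at ρ = .35.** The ratio is (k/m)² × V pooled / V adjusted.

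| Outcomes | k | Fraction estimated | V pooled | V adjusted | Sample ratio |
|---|---|---|---|---|---|
| Diet, activity | 4 | 3/4 | .5125 | .4442 | 2.05 |
| Weight, waist, BP | 3 | 2/3 | .5667 | .5525 | 2.31 |
| Laboratory | 2 | 1/2 | .675 | .8775 | 3.08 |

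The five-visit planning model would give 4/5. Under assumed AR(1) or random-slope covariances, the total weight on post-baseline visits for these schedules was 0.43 to 0.73, so the dilution is similar or somewhat worse. A small mixed-model simulation (12 runs, imprecise) gave 0.72, 0.69 and 0.55.

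**Power at 53 per group, pooled versus baseline-adjusted.**

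| Outcomes | Constant 0.805 | Pattern 2 shape, genetics acting only with coaching |
|---|---|---|
| Diet, activity | .80 vs .98 | .91 vs >.99 |
| Weight, waist, BP | .64 vs .96 | .86 vs >.99 |
| Laboratory | .32 vs .81 | .40 vs .90 |

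For laboratory outcomes with 0.805: pooled 0.4025/√(4 × .675/53) = 1.783, and 1.783 − 2.241 = −0.458, power .32. Adjusted 0.805/√(4 × .8775/53) = 3.128, power .81. For power .80 the pooled test needs 159 per group (127 if the interaction is 0.90); the adjusted test needs 52 (42).

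The gain is not all covariate adjustment. With a constant 0.805, dropping the baseline row without adjustment already gives .95, .91 and .76.

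**Sensitivity to the unknown cell means.** If the control group instead stays at 0.05 throughout, pooled D is 0.32 and n is 178 per group, far from the stated 44. Power at 53 would be .42 vs .75, .72 vs .98 and .40 vs .90. The laboratory result is unchanged, because both splits give 0.90 at 12 months.

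**The case against.** The criticised model is assembled from two sections, not written in one. The pooled test appears only in 8.1, as one branch of an and/or list. Section 8.2 speaks of trajectories, names a three-way test that baseline would not dilute, and leaves the type of longitudinal model to preliminary analyses. This stands as a limit: pooling over baseline is an inference from the pooled means, the time-0 level and the missing baseline covariate. It does not remove the point, because nothing in the primary analysis text specifies change scores, a baseline covariate or constrained baseline means.

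A reader might infer that this is the trial's only remaining test of synergy. The documents do not settle that, since 8.2 still carries the three-way expectation that 8.1 removed.

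A reader might also infer that the planned 80% power is wrong throughout. For diet and activity it is not shown to be: 44 per group appears already to carry the baseline zero, and the pooled power at 53 is .80 or .91 under the two effect shapes that agree with 44. The constant 0.805 is also rough, since it averages in a 6-week visit at which Table 2 schedules none of these outcomes. With the pattern 2 shape, the clinic measures exceed 80% as well. What stands is relative inefficiency for those outcomes and a real shortfall for laboratory outcomes.

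**Conclusion.** The point holds as a loss of efficiency and scale, not of validity. With no interaction at any visit, the pooled contrast also has expectation zero, so type I error is unaffected. If 8.1 and 8.2 are followed together, the retained coaching-by-genetics term and the pooled direct effects estimate 3/4, 2/3 or 1/2 of a constant post-baseline effect, depending on the outcome. The test then needs roughly two to three times the sample of a baseline-adjusted one.

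The loss is serious only for the laboratory outcomes, which have one post-baseline visit, whereas the power was planned on five visits including baseline. The fractions rest on complete data, equal visit weights and a constant effect. The power figures rest also on two-sided alpha, SD 1 and inferred interaction sizes, because the cell means are not given in the text.

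**What to change.** - In 8.2, replace the leftover three-way expectation with the two-way tests that 8.1 retains.
- Define coaching-by-genetics and each direct effect as a 1-df contrast of the average post-baseline difference: over 3, 6 and 12 months for diet and activity, 6 and 12 for clinic measures, and 12 for laboratory values.
- Choose one of two models. Either use only post-baseline visits as outcomes with the baseline value as a covariate, or keep baseline in the outcome vector with its means constrained equal across arms.
- In 8.1, restate the 176–196 for that contrast, give the four cell means behind it, and show the laboratory outcomes separately.

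The cost is SAP wording and a re-run of the power table, with no new data or participants. Those with no post-baseline value would contribute essentially nothing to the contrast, which is a negligible loss. The change removes the baseline dilution but does not make outcomes fully comparable: averages over different sets of visits remain different quantities if the effect varies over time.
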